## 2 Study Design Overview and Protocol History

### Version 1.0 of the PREVAC Protocol

Version 1.0 of PREVAC described the plan to compare three vaccine strategies with placebo in adults and children for immunogenicity and safety. The three vaccine strategies were:

- 1) Ad26.ZEBOV (prime) (0.5 mL) followed by an MVA boost (0.5 mL) at 56 days;
- 2) rVSV (prime) (1 mL) with a placebo (1 mL) boost at 56 days; and
- 3) rVSV (prime) (1 mL) with a rVSV boost (1 mL) at 56 days.

There were two placebo groups, one with a syringe fill volume of 0.5 mL to match the fill volumes of the Ad26.ZEBOV and MVA vaccines and the other with a fill volume of 1 mL to match the fill volume for the rVSV vaccine. We referred to this plan as the 5-arm randomization.

Version 1.0 of PREVAC was not implemented.

### Version 2.0 of the PREVAC Protocol

In January 2017, prior to beginning Version 1.0 of PREVAC, the NIH informed the co-sponsor and collaborators in PREVAC of a suspension of enrolment in a study of the rVSV vaccine in at-risk health care workers at the NIH Clinical Center. The investigator of the NIH study found that among 9 participants enrolled and vaccinated with the rVSV vaccine, 3 developed signs and symptoms of arthritis in the knee 10-14 days following vaccination. The lot of vaccine in the NIH study was the same lot of rVSV vaccine provided for PREVAC.

The investigation by Merck into the vaccine lot and discussions of next steps, which potentially could include the preparation of a new vaccine lot, was likely going to take

some time. Because the sites in Guinea and Liberia were prepared to begin enrolment, the PREVAC team decided to modify the PREVAC protocol and begin the trial with the Ad26.ZEBOV/MVA-BN-Filo vaccine strategy and matching placebo (Figure 1). Version 2.0 of the protocol was issued on February 27, 2017. The plan was to move to the 5 arm randomization as soon as possible after Merck completed their review of the batch of rVSV vaccine to be used in PREVAC. Enrollment in Version 2.0 of PREVAC began on March 27, 2017 and ended on July 18, 2017 with 537 participants enrolled, 496 adults and 41 children. These participants were enrolled by 2 sites in Guinea, Landreah and Maferinyah, and by one site in Liberia, Redemption.

#### Version 3.0 of the PREVAC Protocol

Merck's investigation of the lot of the rVSV vaccine used in the NIH study determined that the lot met all manufacturing parameters and all criteria associated with the product. Merck also reviewed reports of arthritis from all completed and ongoing studies of the rVSV vaccine and concluded that the reports of arthritis were generally consistent with other reports of arthritis from their program.

At the request of the PREVAC team, Merck provided another lot of the vaccine for PREVAC that is different from the lot used in the NIH study. The certificate of analysis of the new rVSV vaccine lot indicated a test result of  $1.3 \times 10^8$  pfu/mL, a dose which was higher than that used in the PREVAIL I trial in Liberia ( $2 \times 10^7$ ).

Variation in titer/potency in live virus vaccines is common. Vaccine manufacture and release for potency is based upon defined specifications and always encompasses a range, routinely with a lower and upper limit. The lower limit, referred to as the nominal dose, is determined during development and is defined by the lowest dose for which there is demonstrated efficacy. A test result higher than the nominal dose is routine amongst live attenuated vaccines because the lower limit for potency must still be valid at the end of shelf-life in order to ensure that the vaccine is still efficacious up until its defined expiry.

Since there were limited numbers of children in previous studies of the rVSV vaccine and the dose used was similar to PREVAIL I (the diluted dose), it was decided to use a measured approach and give the rVSV vaccine at a 2-fold dilution (approximately  $5 \times 10^7$  pfu/mL). Version 3.0 of the protocol used this dose of the Merck rVSV vaccine. We refer to this as the diluted dose. The 5-arm Version 3.0 design is depicted in Figure 2.

Both adults and children were enrolled under Version 3.0; however, the focus was on the enrollment of children. The enrolment of children began with those 12-17 years, and proceeded to those 5-11 and 1-4 years in a sequential fashion after safety reviews by the DSMB. When the DSMB determined that the two prime vaccines (both the diluted rVSV vaccine and the Ad26.ZEBOV vaccine) were safe in all age groups, the design was modified to enroll adults and children with the undiluted rVSV vaccine (Version 4.0).

Two sites in Guinea, Landreah and Maferinyah, and one site in Liberia, Redemption, enrolled 1,450 participants (663 adults and 787 children) in Version 3.0 of PREVAC.

#### Version 4.0 of the PREVAC Protocol

The design of Version 4.0 of the PREVAC protocol was similar to Version 3.0 except the undiluted rVSV vaccine was used. This design is depicted in Figure 3.

In Version 4.0, like Version 3.0, the enrolment of children began with those 12-17 years, and proceeded to those 5-11 and 1-4 years in a sequential fashion after safety reviews by the DSMB.

Two sites in Guinea, Landreah and Marferinyah, one site in Liberia, Redemption, 2 sites in Mali, UCRC and CVD, and one site in Sierra Leone, Mambolo, enrolled 2,802 participants in Version 4.0. Of these 2,802 participants, 1,401 were adults and 1,401 were children. In each of 3 age groups, 1-4, 5-11 and 12-17 there were 467 children enrolled.

#### Follow-up and Data Collection

The follow-up visit schedule was the same for Versions 2.0, 3.0 and 4.0. Following randomization, all participants were seen at 7, 14, 28, 56 and 63 days, and at 3, 6, and 12 months. Participants continue to be seen at 24, 36, 48 and 60 months.

The data collection plan is also the same with three exceptions for children: 1) under Version 4.0, temperature was measured each day in the week after prime and booster vaccination; 2) clinical significant laboratory abnormalities were identified by the site and reported on the case report form; and 3) there was greater standardization across sites for the daily collection of symptoms and injection site reactions each day of the week after prime and booster vaccination.

[figure not shown]
Summary

Table 1 summarizes the different versions of the PREVAC protocol that have been planned and implemented. Version 1.0 was not implemented. In versions 2.0, 3.0 and 4.0, data on safety and immunogenicity will be available for the rHAd26 prime/MVA boost vaccine and matching placebo. Versions 3.0 and 4.0 will also provide safety and immunogenicity data for the two rVSV vaccine strategies and matching placebo.

[figure not shown]
**Table 1. Summary of PREVAC Protocol Versions**

PREVAC Protocol Version	Date of Protocol	No. of Vaccine Groups	Vaccine Groups
1.0	October 8, 2016	5	rHAd26/MVA boost, rVSV with and without boost, and matching placebo groups
2.0	February 27, 2017	2	rHAd26/MVA boost and matching placebo
3.0	May 5, 2017	5	rHAd26/MVA boost, diluted rVSV with and without boost, and matching placebo groups
4.0	March 10, 2018	5	rHAd26/MVA boost, undiluted rVSV with and without boost, and matching placebo groups

**Figure 1: PREVAC Version 2.0 Design**

[figure not shown]

**Figure 2: PREVAC Version 3.0 Design**

**Figure 3: PREVAC Version 4.0 Design**

## 2.1 Analysis Set

The analysis set for both adults and children, which will be analyzed separately and combined, includes all participants who were randomized (and, who by definition, received the prime vaccination). This analysis set will be used for all analyses.

All participants enrolled in Version 4.0 met the eligibility criteria.

### 2.1.1 Baseline Characteristics

Baseline characteristics will be summarized by vaccine/placebo group (4 groups) and overall. Baseline characteristics will be shown separately for adults and children.

The following baseline characteristics will be summarized:

- Age
- Gender
- Body mass index (adults)
- Arm circumference (children, 1-4 years)
- HIV (%) (adults)
- Syphilis (%)
- Ebola IgG titer; median, IQR, percent “elevated”
- Site and country of enrolment

Summaries for continuous-valued outcomes by treatment group will include N and mean, SD or median, 25th and 75th percentiles. Summaries for categorical outcomes will include N and %.

P-values for comparisons of baseline characteristics between treatment groups will not be provided.

### 2.1.2 Data Completeness (to be used in Flow Diagram)

The following reports will be provided for adults and children by treatment group:

- Follow-up visit attendance (N and % of those alive).
- Number and percent of those alive with a baseline, 28 day, 6 month and 12 month antibody result.
- Number and percent who withdrew consent.

**Note: Among 1,401 adults, 1,335 (95.3%) attended the 12 month visit. Among 1,401 children, 1,352 (96.5%) attended the 12 month visit.**

### 2.1.3 Booster Vaccination

The number and percent of participants who received the booster vaccination and the reason the booster was not received will be summarized, overall and by age group. In addition, the distribution of the number of days after randomization that the booster

vaccination was administered will be summarized.

**Note: Among 1,401 adults randomized, 1,325 (95%) received a boost. Among 1,335 adults who attended the 12 months visit, 1,286 (96%) received a boost. Among 1,401 children randomized, 1,372 (98%) received a boost. Among 1,352 children who attended the 12 month visit, 1,334 (99%) received a boost.**

#### 2.1.4 Immunogenicity outcomes

The primary endpoint specified in the protocol by the PREVAC group is the percentage of antibody responders at 12 months. An antibody responder at 12 months is defined as a participant who experiences a 4-fold increase in antibody level from baseline (i.e., a .6 increase on the  $\log_{10}$  scale) and for whom the antibody level at 12 months is  $\geq 200$  EU/mL. With this definition, participants with a missing baseline or 12 month result will be excluded. Also, with this definition, there will be no exclusion of participants with elevated antibody levels at entry.

Each of the 3 vaccine strategies will be compared with the pooled placebo group at the 0.0167 (2-sided) level of significance. Analyses will be carried out for adults and children separately and combined.

This same definition will be used for defining responders at 7, 14, 28, 56, and 63 days and at 3 and 6 months. For the comparisons with the pooled placebo group at 7, 14, 28, and 56 days, the two rVSV strategies will be combined. The two pair-wise comparisons at these time-points, each vaccine strategy versus pooled placebo, will be carried out at the 0.025 (2-sided) level of significance.

As a sensitivity analysis, for the above analyses based on responders, participants with an antibody level  $\geq 200$  EU/mL at baseline will be excluded.

The following additional summaries of antibody levels will be carried out, separately for children and adults:

- Geometric mean titers at 7, 14, 28, 56, and 63 days, and 3, 6 and 12 months separately for adults and children. Comparison groups will be defined as above for version 4.0 participants at day 63 and months 3 and 6. For 7, 14, 28, and 56 days, the rVSV vaccine groups with and without the boost will be combined. Analysis of covariance with stratification by site and with baseline  $\log_{10}$  antibody level as a covariate will be used to compare each vaccine group versus the pooled placebo for  $\log_{10}$  antibody levels at each follow-up visit (geometric mean ratios will be cited).
- Fold increase from baseline to 14 and 28 days, and 6 and 12 months (<2, 2 to < 4, 4 to < 8, 8 to <16,  $\geq 16$ ).
- Box plots of antibody levels at 14 and 28 days, and 6 and 12 months. For days 14 and 28 the rVSV vaccine groups with and without the boost will be combined.

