### 2.4. Secondary objectives

The following secondary objectives will be assessed. Unless otherwise stated, the objectives will be addressed separately for adults and children:

- To compare the groups given the Ad26.ZEBOV prime vaccine and the rVSVΔG-ZEBOV-GP prime vaccine (both rVSVΔG-ZEBOV-GP groups combined) each with the pooled placebo group for the antibody response 14 days after randomization (prime vaccination) (immediacy of response).
- To compare each of the vaccine groups versus the pooled placebo group for the antibody response profile using measurements at 7, 14, 28, 56, 63 days and at 3, 6 and 12 months after randomization.
- To compare each of the vaccine groups with the pooled placebo group for SAEs at 12 months (see section [4.1.3](#)).
- To compare the groups given the Ad26.ZEBOV prime vaccine and the rVSVΔG-ZEBOV-GP prime vaccine (both rVSVΔG-ZEBOV-GP groups combined) each with the pooled placebo group for the percent with injection site reactions and AEs graded for severity, including targeted symptoms, during the first week following randomization (including the daily contacts for children only).
- To compare the groups given the Ad26.ZEBOV prime vaccine and the rVSVΔG-ZEBOV-GP prime vaccine (both rVSVΔG-ZEBOV-GP groups combined) each with the pooled placebo group for percent reporting injection site reactions and AEs graded for severity, including targeted symptoms, following prime vaccination at the vaccination visit, and through 7, 14, and 28 days after the prime vaccination.

- To compare each of the vaccine groups with the pooled placebo group for changes from baseline in biochemical markers and complete blood count (CBC) measurements at 7 days after randomization (children only).
- To compare the rHAd26/MVA and rVSVΔG-ZEBOV-GP boost strategies with the pooled placebo group for changes from baseline in biochemical markers and CBC measurements at 63 days after randomization (children only).
- To compare the rHAd26/MVA and rVSVΔG-ZEBOV-GP boost strategies with the pooled placebo for percent with injection site reactions and AEs graded for severity, including targeted symptoms, immediately following the booster vaccination and through month 3 (approximately 35 days after the booster vaccination).
- To compare the three vaccine strategies versus the pooled placebo group for long-term antibody response at 24, 36, 48 and 60 months following randomization (if funding permits).

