## 7. EVALUATION

### 7.1. Planned data analyses

Final analyses will be carried out according to a statistical analysis plan that is updated prior to unblinding. The planned analyses below only describe those planned for participants enrolled under Version 4.0. Separate analyses will be carried out for participants enrolled under Version 2.0 and 3.0. These analyses and analyses which will be pooled across protocol versions are described in the statistical analysis plan.

Prior to unblinding, the analysis plan for the immunogenicity substudy ([Appendix D](#)) and the viral shedding substudy ([Appendix E](#)) will also be finalized.

For the purposes of regulatory filings there is a specific primary objective for each participating pharmaceutical company involving a single follow-up time point and the use of a validated assay for immunogenicity testing. Thus, the two companies may also prepare a statistical analysis plan prior to unblinding and regulatory filing that describes analysis plans for their primary objective (e.g., comparisons with matched placebo for immunogenicity due to gamma irradiation of a subset of specimens) as well as plans for controlling type 1 error for investigations of secondary endpoints and subgroups.

The following plan outlines data analyses that will be carried out during the trial by the unblinded statisticians for the independent DSMB.

Adults and children will be analyzed separately and combined. Baseline characteristics and follow-up completeness will be summarized by vaccine group.

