SAEs will be classified by system organ class according to MedDRA®. The total number of events and the number of participants with at least one event will be reported. Mantel-Haenszel chi-square statistics will be used for each pair-wise comparison of the number of participants with an SAE through 12 months of follow-up; time-to-event methods, e.g., Kaplan-Meier, Cox regression, will also be used to compare groups for SAEs over the 12 month follow-up period. Analyses will also be carried out for SAEs judged to be related to the vaccine. If follow-up is extended to 60 months, similar analyses will be performed for SAEs reported through 60 months.

Each vaccine group will be compared with the pooled placebo group using Mantel-Haenszel chi-square tests and time-to-event methods for diagnoses of laboratory-confirmed malaria through 12 months of follow-up.

For safety and efficacy outcomes assessed before the booster at 56 days, the two groups given the rVSVΔG-ZEBOV-GP prime vaccination will be combined for comparisons with pooled placebo group. For outcomes that are assessed after 56 days, each of the three vaccination strategies will be compared with the pooled placebo group.

Mantel-Haenszel chi-square tests will be used to compare each vaccine with placebo for the percent with grade 3 or 4 AEs and with targeted symptoms reported at 7, 14, and 63 days. Similar methods will be used to compare injection site reactions reported immediately following prime vaccination and at 7 and 14 days. Likewise, treatment differences in injection site reactions reported immediately following booster vaccination and through day 63 (7 days after booster vaccination) will be summarized with similar methods. In the event that there is evidence that safety outcomes differ between the two placebo groups, analyses will also be performed for each vaccine versus its matched placebo.

Longitudinal mixed models will be used to compare log-transformed antibody levels collected at multiple follow-up time points during follow-up. Results will be summarized as geometric means and geometric mean ratios. These analyses will be carried out among participants who did not have elevated antibody levels at baseline. Baseline titer level will be included as a covariate. These analyses will be supplemented with scatter plots that display fold increases in antibody titers, line plots, box plots and reverse cumulative distributions of antibody levels at each visit for each vaccine group.

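### SAP 2.1.4 replaces the protocol's longitudinal mixed model with separate per-visit ANCOVAs, leaving no joint analysis of the antibody profile and no stated protection against unequal arm variances

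*SAP*

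**What the plan says.** Protocol 2.4 sets a secondary objective: "To compare each of the vaccine groups versus the pooled placebo group for the antibody response profile", using eight visits from day 7 to month 12. Protocol 7.1 gives a method: "Longitudinal mixed models will be used to compare log-transformed antibody levels collected at multiple follow-up time points during follow-up". Results are to be reported as geometric means and GMRs, with baseline titre as a covariate. On the population it says: "These analyses will be carried out among participants who did not have elevated antibody levels at baseline". It states no covariance structure and no arm-specific variance.

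SAP 2.1.4 mentions no mixed model. It plans geometric mean titres at the same eight visits, and an ANCOVA stratified by site in which baseline log10 "antibody level as a covariate will be used to compare each vaccine group versus the pooled placebo for" log10 levels at each follow-up visit, with GMRs cited. For days 7 to 56 the two rVSV arms are combined. Responder comparisons are planned at all eight visits, with fold-increase categories and box plots at selected ones. The section does not say whether the ANCOVA is fitted pairwise or to all arms together, which variance estimator is used, how a GMR interval is formed, or how missed visits are handled.

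**The concern.** Durability and kinetics of the immune response are stated purposes of the trial (Protocol Synopsis, Background and Rationale). A separate ANCOVA at each visit estimates the vaccine effect at that visit. It does not test how the effect changes over time, and it does not use the correlation between one person's titres. The SAP governs the final analysis, so a model it leaves out is no longer pre-specified.

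The second issue is the error bars. An ordinary ANCOVA pools one residual variance over the arms in the model. A vaccine arm that mixes responders and non-responders could well vary more than placebo: in PREVAIL I, 79.5% of rVSV recipients and 6.8% of placebo recipients were responders at 12 months (Protocol 2.7). With unequal arm sizes, pooling then gives GMR standard errors that are too small for some contrasts or too large for others.

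**Working it through.** **Plan's own figures.** Twelve-month attendance in SAP 2.1.2 reproduces: 1,335/1,401 = 95.3% of adults and 1,352/1,401 = 96.5% of children, so 4.7% and 3.5% did not attend.

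**Inputs.** Allocation 2:1:2:1:1 with 1,400 per age stratum (Protocol 2.1 and 2.7) gives Ad26/MVA 400, rVSV without boost 400, rVSV with boost 200, and pooled placebo 400. The combined rVSV arms have 600. Residual SDs on the log10 scale are assumptions: 0.5 vaccine and 0.2 placebo, or 0.4 and 0.3.

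**Formulas.** For a vaccine arm of size nv and placebo of size np:
- true SE = sqrt(sv²/nv + sp²/np)
- model SE = sqrt(s² × (1/nv + 1/np)), where s² is the size-weighted mean variance of the arms in the model
- coverage of a nominal 95% interval = 2Φ(1.96 × model SE / true SE) − 1

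**Pairwise fit, SDs 0.5/0.2**
- 200 versus 400: s² = (200×0.25 + 400×0.04)/600 = 0.110. Model SE = sqrt(0.110×0.0075) = 0.0287. True SE = sqrt(0.00125 + 0.00010) = 0.0367. Ratio 0.78, coverage about 87%.
- 600 versus 400: s² = (600×0.25 + 400×0.04)/1,000 = 0.166. Model SE = 0.0263, true SE = 0.0227. Ratio 1.16.
- 400 versus 400: the two SEs are equal. Ratio 1.00.

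**All-arm fit, SDs 0.5/0.2.** s² = (1,000×0.25 + 400×0.04)/1,400 = 0.19.
- 200 versus 400: sqrt(0.19×0.0075/0.00135) = 1.03
- 400 versus 400: sqrt(0.19×0.005/0.000725) = 1.14
- 600 versus 400: sqrt(0.19×0.004167/0.000517) = 1.24

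**SE ratios (model/true)**

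| Contrast | Pairwise 0.5/0.2 | Pairwise 0.4/0.3 | All-arm 0.5/0.2 | All-arm 0.4/0.3 |
|---|---|---|---|---|
| 200 v 400 (boosted rVSV) | 0.78 | 0.91 | 1.03 | 1.01 |
| 400 v 400 | 1.00 | 1.00 | 1.14 | 1.06 |
| 600 v 400 (combined rVSV) | 1.16 | 1.06 | 1.24 | 1.09 |

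For 0.4/0.3 the all-arm s² is (1,000×0.16 + 400×0.09)/1,400 = 0.14. The pairwise ratio of 0.91 corresponds to about 93% coverage.

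**Opposite direction.** If placebo were the more variable arm (vaccine/placebo SD ratio 0.5), the shortfall moves. Pairwise 200 versus 400 covers 98.4%, pairwise 600 versus 400 covers 91.8%, and all-arm 400 versus 400 covers 90.9%.

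**Does a robust variance cure it?** A per-visit four-arm ANCOVA with six sites and a baseline covariate was simulated, 2,000 replicates per setting, with HC3 standard errors. At vaccine/placebo SD ratios of 1, 1.5 and 2, coverage was 95.3%, 95.1% and 94.1% for 400 versus 400, and 95.0%, 95.0% and 95.1% for 200 versus 400. Monte Carlo error is about 0.5 percentage points (sqrt(0.95×0.05/2,000)).

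**Missed visits.** With 4.7% of an arm missing and absentees differing by an assumed 0.1, 0.3 or 0.5 log10, that arm's geometric mean shifts by 10^(0.047×difference), a factor of 1.01, 1.03 or 1.06.

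**The case against.** The protocol itself allows the change: "Final analyses will be carried out according to a statistical analysis plan that is updated prior to unblinding". It also introduces the outlined methods with "The following plan outlines data analyses that will be carried out during the trial by the unblinded statisticians for the independent DSMB", so the mixed model could be read as a monitoring tool only. Per-visit ANCOVA with baseline adjustment is a standard way to obtain GMRs, and the SAP was written before unblinding. The SAP was therefore entitled to make the change. But the same part of Protocol 7.1 holds the primary 12-month comparison, so the monitoring-only reading is weak, and entitlement does not supply a reason.

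Four stronger readings are tempting, and the documents do not support them.
- A reader might infer that the profile objective has no analysis. It has GMTs, adjusted GMRs and responder comparisons at every visit it names; only a joint analysis is missing.
- A reader might infer that the boosted-rVSV intervals are simply too narrow. That needs a pairwise fit and a more variable vaccine arm. SAP 2.1.5.8 uses vaccine indicators in one regression for laboratory data, and under that reading this contrast is near nominal. Nor did dropping the mixed model create the variance gap: the protocol's model sets no arm-specific variance either.
- A reader might infer that one missed visit discards a participant's other samples. The rule that "participants with a missing baseline or 12 month result will be excluded" is written for the 12-month responder endpoint. A per-visit ANCOVA would lose that participant only at the missed visit.
- A reader might compute a familywise error of 1 − 0.975⁴ × 0.9833⁴ = 15.5% over eight visits. This assumes independent tests on repeated titres from the same people and no effect at any visit, and a mixed model reporting a GMR at each visit would not remove it.

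**Conclusion.** The point holds in limited form. The SAP omits the protocol's longitudinal model without explanation, and the profile objective is left with visit-by-visit comparisons only. Separately, an ordinary ANCOVA would give miscalibrated GMR standard errors for at least some contrasts under either fit if arm variances differ. At SDs 0.5/0.2 the ratios run from 0.78 to 1.16 pairwise and from 1.03 to 1.24 all-arm; at 0.4/0.3 they run from 0.91 to 1.06 and from 1.01 to 1.09. These sizes rest on assumed SDs and on reading an unqualified ANCOVA as common-variance. Equal arms fitted pairwise are unaffected. The 12-month responder endpoint does not depend on this, and bias from missed visits is likely small. It is a secondary-analysis weakness worth correcting because the correction is nearly free.

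**What to change.** In SAP 2.1.4, before unblinding:
- Use heteroscedasticity-robust (for example HC3) or arm-specific variances for each visit's GMR, and state its confidence interval. Say whether the fit is pairwise or all-arm and who contributes at each visit.
- Reinstate the protocol's mixed model as the analysis of the antibody profile: arm by visit, baseline level and site, with variances allowed to differ between vaccine and placebo, and a joint arm-by-visit test for each vaccine.
- Settle its population. The protocol's model excludes participants with elevated baseline antibody, whereas the SAP uses all randomised participants and writes its baseline-exclusion sensitivity analysis for responders only.

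The cost is one SAP paragraph and some programming. No new data are needed, and the mixed model is already in the protocol. The robust variance alone repairs the intervals; the mixed model is needed for the joint profile analysis and for using partly observed participants.
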